6.5.4.4 Anemia

Risk management measures in addition to routine laboratory tests will include:

- Subjects must enter the trial with Hgb values at least 9 g/dL
- Routine monitoring of Hgb, red blood cells, and hematocrit will be performed every week up to Week 5 and then every 2 weeks thereafter (prior to treatment)
- RBC morphology will be assessed in the case of anemia onset caused by hemolysis, or other unknown causes
- Instructions for trial treatment discontinuation or modification in case of anemia will be provided, briefly described here:
- o If decreased Hgb below 8 g/dL does not return to 9 g/dL (the entry criterion at screening) or changes in associated red blood cell parameters during such a Hgb decrease that do not resolve within 14 days without blood transfusion or erythroid growth factor use, the subject is permanently withdrawn from trial treatment (pertains only to the 21-day DLT period). Furthermore, the subject may require additional treatment for anemia.
- o Especially if Hgb < 7 g/dL, the Investigator should consider blood transfusion.
- o In case of any Hgb < 8 g/dL, the Investigator should use discretion to initiate anemia work up, including Coombs, haptoglobin, indirect bilirubin and peripheral smear, and prothrombin time, activated partial thromboplastin time, INR; Hgb, red blood cells, and hematocrit are to be closely monitored.
 - If a subject experiences significant anemia, then the amount of blood to be drawn may be reduced by not taking blood at selected time points for soluble factors and TGFβ. The decision to reduce the time points for these biomarkers will be taken by the Investigator in consultation with the Medical Monitor. This will be documented. Blood will continue to be taken as scheduled for safety analyses, PK, anti-drug antibodies (ADAs).

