5.1.3.3 Dose-Limiting Toxicity

A DLT is defined as any Grade \geq 3 AE, with the exceptions described hereafter, assessed as related to IMP by the Investigator and/or Sponsor (ie, Grade \geq 3 adverse drug reaction [ADR]; grading

CONFIDENTIAL INFORMATION

according to the National Cancer Institute (NCI) Common Terminology Criteria for Adverse Events Version 4.03 [CTCAE v4.03]) occurring in the DLT evaluation period (21 days after first administration of MSB0011359C) confirmed by the SMC to be relevant for the IMP treatment. The SMC recognizes that in the absence of prior human experience with MSB0011359C, a conservative approach will be adopted in ascribing the relevance of the treatment-related toxicity to IMP. Treatment-related SAEs will be ascribed as related to drug except where a clear relationship to the underlying disease or recognized comorbidities is evident.

A DLT is defined as the following:

Any Grade \geq 3 AE that is related to MSB0011359C, occurring during the DLT evaluation period (21 days after administration of MSB0011359C), **except** for those listed below. Also, elevated alanine aminotransferase (ALT) or aspartate aminotransferase (AST) 3 times the upper limit of normal (ULN) and a concomitant elevation of bilirubin 2 times the ULN attributable to study drug constitutes a DLT.

- Grade 3 infusion-related reactions resolving within 6 hours from the end of infusion and controlled with medical management.
- Transient (≤ 6 hours) Grade 3 flu-like symptoms or fever, which is controlled with medical management.
- Transient (≤ 24 hours) Grade 3 fatigue, local reactions, headache, nausea, emesis that resolves to Grade < 1.
- Any Grade ≥ 3 drug-related amylase or lipase abnormality that is not associated with symptoms or clinical manifestations of pancreatitis.
- Grade 3 Hgb decrease (< 8.0 g/dL) that resolves to at least 9 g/dL within 14 days or the changes in the associated RBC parameters resolve within 14 days without blood transfusion or erythroid growth factor use.
- Malignant skin lesion that is local and can be resected with negative resection margin.

Dose-limiting toxicities that require treatment discontinuation are described in Section 5.1.7.2.

Subjects who do not complete the DLT observation period for reasons other than a DLT will be replaced.

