5.1.7 Dose Modification and Adverse Drug Reactions Requiring Treatment Discontinuation

5.1.7.1 Dose Modification

The dose of MSB0011359C will be calculated based on the weight of the subject determined on the day prior to or the day of each drug administration.

Each subject will stay on the MSB0011359C dose level assigned in the trial unless treatment needs to be stopped. Dosing modifications (changes in infusion rate) and dose delays are described in Section 5.1.7.2 and Section 6.5.4 and subsections. There are no dose reductions.

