5.1.7.2 Adverse Drug Reactions Requiring Treatment Discontinuation

Certain ADRs, defined in this trial as any AE assessed as related to MSB0011359C by the Investigator and/or Sponsor, may require permanent treatment discontinuation of MSB0011359C (listed below). For certain ADRs assessed to be immune-related, Table 5 criteria may supersede this section. These criteria may allow the subject to continue on study if medically indicated after consultation with Medical Monitor.

Any Grade 4 ADRs require permanent treatment discontinuation except for single laboratory values out of normal range that do not have any clinical correlate, and resolve to Grade ≤ 1 within 7 days with adequate medical management.

Any Grade 3 ADRs require treatment discontinuation except for any of the following:

• Transient (≤ 6 hours) Grade 3 flu-like symptoms or fever, which is controlled with medical management.

CONFIDENTIAL INFORMATION

- Transient (≤ 24 hours) Grade 3 fatigue, local reactions, headache, nausea, emesis that resolves to ≤ Grade 1.
- Tumor flare phenomenon defined as local pain, irritation, or rash localized at sites of known or suspected tumor.
- Any Grade ≥ 3 drug-related amylase or lipase abnormality that is not associated with symptoms or clinical manifestations of pancreatitis. The trial Medical Monitor should be consulted for such Grade ≥ 3 amylase or lipase abnormalities. If the amylase or lipase abnormality not associated with symptoms or clinical manifestations of pancreatitis has not resolved to Grade ≤ 1 within the subsequent 2 cycles (28 days), the subject should permanently discontinue treatment with MSB0011359C.
- Grade 3 Hgb decrease (< 8.0 g/dL) that is clinically manageable with blood transfusions or erythroid growth factor use does not require treatment discontinuation. During the 21-Day DLT period, a Grade 3 Hgb decrease (< 8.0 g/dL) will require treatment discontinuation, unless it resolves to at least 9 g/dL within 14 days or the changes in the associated RBC parameters resolve within 14 days without blood transfusion or erythroid growth factor use.
- Increases in Eastern Cooperative Oncology Group performance status (ECOG PS) ≥ 3 that resolves to ≤ 2 by cycle Day 1 of the next cycle (infusions should not be given if the ECOG PS is ≥ 3 on the day of IMP administration and should be delayed until ECOG PS ≤ 2).

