- Keratoacanthoma and squamous cell carcinoma of the skin. Any suspicious skin lesion should be biopsied and be surgically removed. The Study Medical Monitor should be consulted.
- Grade 3 or 4 dematological irAEs, treatment should be delayed and treatment started according to Table 5, if condition improves to Grade 1, treatment may be resumed. If ≥ 2 consecutive doses are missed, the Medical Monitor should be consulted.
- Grade 3 or 4 symptomatic endocrinopathies (eg, thyroiditis or hypophysitis), treatment should be delayed and treatment started according to Table 5, if condition improves to Grade 1, treatment may be resumed. If ≥ 2 consecutive doses are missed, the Medical Monitor should be consulted
- Other immune-related ADRs, see Table 5.

Any Grade 2 ADR should be managed as follows:

- If a Grade 2 ADR resolves to Grade ≤ 1 by the last day of the current cycle, treatment may continue.
- If a Grade 2 ADR does not resolve to Grade ≤ 1 by the last day of the current cycle but is manageable and/or not clinically relevant, the ADR should be discussed with the medical monitor. Based on the discussion, it is possible that the infusion will be given on the following cycle. If at the end of the following cycle, the event has not resolved to Grade 1,

CONFIDENTIAL INFORMATION

another discussion should occur with Medical Monitor to consider permanently discontinuing treatment with MSB0011359C.

- Upon the second occurrence of the same Grade 2 ADR in the same subject (except for fatigue and hormone insufficiencies that can be managed by replacement therapy), continuation of treatment with MSB0011359C has to be discussed with the medical monitor and may lead to permanently discontinuation.
- Infusion-related reactions and hypersensitivity reactions (Grades 1 to 4) should be handled according to the guidelines provided in Section 6.5.4.1 and Section 6.5.4.2, respectively.
- Anemia should be handled according to the guidelines provided in Section 6.5.4.4.
- If immune-related ADRs, see Table 5.

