5.5 Criteria for Subject Withdrawal

5.5.1 Withdrawal from Trial Treatment

Subjects will be withdrawn from trial treatment for any of the following reasons:

- Confirmed PD per RECIST 1.1: Subjects should continue treatment beyond the initial determination of PD, through their next tumor assessment, provided:
- a. There are no new Grade 2 or greater symptoms or significant worsening of existing symptoms.
- b. There is no decrease in ECOG PS.
- c. In the opinion of the Investigator, the subject does not require new anticancer therapy.
 - Subjects should be discontinued from treatment thereafter if further evidence of PD; however, continued treatment is possible in consultation with the Medical Monitor.
 - Occurrence of an exclusion criterion, which is clinically relevant and affects the subject's safety, if discontinuation is considered necessary by the Investigator and/or Sponsor.
 - Therapeutic failure requiring urgent additional cancer therapy.
 - Occurrence of any Grade \geq 3 ADRs or repetitive Grade 2 ADRs as defined in Section 5.1.7.2.
 - Occurrence of AEs, at the Investigator's discretion.

CONFIDENTIAL INFORMATION

- Pregnancy.
- Use of prohibited concomitant drug, as defined in Section 6.5.2, where the predefined consequence is withdrawal from the IMP.
- Non-adherence/noncompliance to the trial protocol or trial requirements (see Section 6.9).
- Withdrawal of consent.
- Participation in any other trial.

For subjects who miss ≥ 2 consecutive doses for medical reasons, the Medical Monitor should be consulted.

Subject Replacement

For the dose escalation part, subjects with the following events during the DLT observation period (see Section 5.1.3.3 and Section 5.5.2) will be considered non-completers and have to be replaced:

- Deviation in MSB0011359C administration of greater than -3 days or +1 day due to reasons other than DLT.
- Other condition that DLT is not evaluable (eg, use of non-permitted medicines as detailed in Section 6.5.2).

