Non-permitted concomitant medication during the study	Concomita nt Medication	Blood transfusions and erythroid growth factors were administered to a patient during the 21 days DLT window during the dose escalation phase.	PDEV44	6.5.2	Medical Review	
Withdrawal from treatm	nent/trial					
Subjects that developed withdrawal criteria whilst on study but were not withdrawn;	Other Criteria	Subject became pregnant, but continued on study.	PDEV45	5.5.1	Medical Review Required. Programmed	
Subjects that developed withdrawal criteria whilst on study but were not withdrawn;	Other Criteria	Subject developed any Grade ≥ 3 ADRs or repetitive Grade 2 ADRs, but continued on study.	PDEV46	5.5.1	Medical Review	
Subjects that developed withdrawal criteria while on the study but were not withdrawn;	Other Criteria	Subjects were not withdrawn despite therapeutic failure requiring urgent additional drug.	PDEV47	5.5.1	Medical Review	
Other Criteria						
Subjects dosing error (≥ +/- 20% assigned dose)	IP Complianc e	Subject had dosing error.	PDEV48	6.2	Programmed	
* Programmed by Data M	Other Criteria	Other protocol deviation	PDEV99	Medical defined	Medical Review	

^{*} Programmed by Data Management team.

Signature Page for VV-CLIN-253237 $\,\mathrm{v}4.0$

Approval	PPD
	-2022 23:39:57 GMT+0000

Signature Page for VV-CLIN-253237 v4.0

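### For Hgb below 8 g/dL in the DLT period, the anemia summary in Protocol 6.5.4.4, read literally, withdraws a subject if either recovery condition fails; 5.1.7.2 stops treatment only if both fail

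*Protocol*

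**What the plan says.** Three places in the Protocol deal with the same event, a drop in Hgb below 8 g/dL during the 21-day DLT period of dose escalation.

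- **5.1.7.2 (discontinuation rule).** A Grade 3 decrease judged drug-related ends treatment in that period "unless it resolves to at least 9 g/dL within 14 days or the changes in the associated RBC parameters resolve within 14 days", the latter with neither transfusion nor erythroid growth factors.
- **5.1.3.3 (DLT definition).** The exception uses the same logic: the event is not a DLT if it is one "that resolves to at least 9 g/dL within 14 days or the changes in the associated RBC parameters resolve within 14 days".
- **6.5.4.4 (anemia).** The subject is permanently withdrawn if, after a fall under 8 g/dL, Hgb "does not return to 9 g/dL (the entry criterion at screening) or changes in associated red blood cell parameters during such a Hgb decrease" are still unresolved at 14 days. The bullet limits itself to the DLT period. Its lead-in reads: "Instructions for trial treatment discontinuation or modification in case of anemia will be provided, briefly described here".

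Some text bears on which section governs. Section 5.5.1 withdraws subjects for Grade 3 or higher "ADRs or repetitive Grade 2 ADRs as defined in Section 5.1.7.2" and does not cite 6.5.4.4. SAP Appendix 1, PDEV46, follows 5.5.1 and records as a deviation a subject who developed such "ADRs or repetitive Grade 2 ADRs, but continued on study". In the other direction, 3.4.3 refers the reader to 6.5.4.4 for anemia risk management, and 5.1.7.2 contains the line "Anemia should be handled according to the guidelines provided in Section 6.5.4.4".

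**The concern.** An investigator with one set of blood counts can find two instructions. Under 5.1.7.2 either recovery lets dosing go on. Under the 6.5.4.4 bullet, taken at its words, either failure ends it permanently.

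Anemia is listed among the important risks in 3.4, and anemia suspected to be drug-related is an adverse event of special interest (7.4.1.1.4), so this is a rule that sites would consult. At stake is whether subjects with the same findings are treated alike, and whether the SAP 16.1.2 counts of events that end treatment reflect one rule. Expedited reporting and review by the Safety Monitoring Committee make divergent practice less likely, but neither tells the site which sentence applies.

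**Working it through.** No sample size, power or error rate is involved, and the plan gives no figure to reproduce. The check compares the logic of the rules.

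**Definitions**
- H: Hgb returns to at least 9 g/dL within 14 days.
- R: the associated RBC changes resolve within 14 days, with neither transfusion nor growth factors.

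**Rules**
- 5.1.7.2: stop unless (H or R), which is stop if (not H) **and** (not R).
- 5.1.3.3: DLT unless (H or R), which is DLT if (not H) **and** (not R).
- 6.5.4.4, literal: withdraw if (not H) **or** (not R).

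The negation of (H or R) is (not H and not R). The bullet keeps the word joining the two limbs and negates each limb, which gives a different condition.

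| H | R | 5.1.7.2 | 6.5.4.4, literal | DLT under 5.1.3.3 |
|---|---|---|---|---|
| yes | yes | continue | continue | no |
| yes | no | continue | withdraw | no |
| no | yes | continue | withdraw | no |
| no | no | stop | withdraw | yes |

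The instructions conflict in 2 of 4 outcomes, those where exactly one recovery occurs. In both, 5.1.3.3 says that the event is not a DLT. The bullet attaches its 14-day limit grammatically only to the RBC limb; this does not remove the conflict.

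**Hypothetical example.** Hgb is 7.8 g/dL on Day 8 and 9.2 g/dL on Day 22 (22 − 8 = 14 days) without transfusion, but the RBC count has not resolved. H holds and R fails. Section 5.1.7.2 lets dosing continue; 6.5.4.4 withdraws the subject. The case is plausible because 9 g/dL is the entry floor, not the subject's own baseline, and the Protocol does not define resolution for the RBC parameters.

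**Timing.** Table 1 gives doses on Days 1, 15 and 29. For a drop first seen on Day 2 or later, the 14 days end on Day 2 + 14 = 16 or later, after both doses in the window. The disagreement therefore normally bears on dosing from Day 29, when the 21-day DLT period is complete.

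**Reach.** The Synopsis plans up to 18 DLT-evaluable escalation subjects, and 5.1.3.2 excludes the expansion cohorts from the DLT criteria. SAP Section 4 says the last participant started on 24 August 2017. Adding 21 days gives 14 September 2017, before both SAP versions (29 September 2020 and 11 April 2022).

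**The case against.** The strongest reply is that no working reader would be misled. Section 5.5.1, which lists the reasons for withdrawal, points to 5.1.7.2. Sections 5.1.7.2 and 5.1.3.3 agree with each other. The 6.5.4.4 bullet announces itself as a brief description, and its second limb lacks a main verb, so it cannot be applied exactly as written.

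Most of this stands. It shows that 5.1.7.2 is the intended rule, and a reader who infers two rules of equal authority goes too far. The cross-references that seem to support equal standing are thin. Section 5.1.7.1 says "Dosing modifications (changes in infusion rate) and dose delays are described in Section 5.1.7.2 and Section 6.5.4 and subsections", which concerns infusion rate and delays rather than discontinuation. The pointer to 6.5.4.4 inside 5.1.7.2 sits in the list on Grade 2 reactions, although a neighboring item in that list covers Grades 1 to 4.

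What does not stand is that the matter is settled in the text. Section 3.4.3 sends readers to 6.5.4.4 without qualification. Section 5.1.7.2 states precedence where it was wanted, letting Table 5 override it for immune-related reactions, but has no such clause for 6.5.4.4.

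The reply is also right on consequence. The 2 of 4 counts logical cases, not patients. The documents give no rate of mixed recovery, and they do not include the full protocol text in force during escalation, so they do not show that any subject was handled under the wrong sentence.

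**Conclusion.** The point holds as a minor drafting error: 6.5.4.4 misstates a stopping rule that 5.1.7.2 and 5.1.3.3 state consistently. Its effect is confined to treatment continuation and descriptive discontinuation counts in at most 18 DLT-evaluable subjects. The number actually affected is unknown. Because all DLT windows had closed, correcting the text clarifies the record and any reuse of the wording; it protects no new subject.

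Three stronger inferences are not supported:

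- **That the DLT count or MTD is compromised.** Section 5.1.3.3 alone defines a DLT, and its exception is not in doubt.
- **That withdrawn subjects would distort the cohorts through replacement.** By the timing above, the DLT period would usually be complete before the rule could act.
- **That a withdrawal under 6.5.4.4 is readily reversible.** Section 7.1.3 permits one re-initiation after an adverse-event discontinuation that has since resolved or is well managed. The Synopsis (treatment duration), 5.1.6 and 7.1.2 bar retreatment where toxicity ended the initial therapy. Retreatment is therefore itself unclear.

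The conclusion assumes the literal reading of the bullet and a Grade 3 drug-related event, the case that 5.1.7.2 addresses.

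**What to change.** Replace the withdrawal sentence in 6.5.4.4 with a cross-reference, for example: *For Hgb decreases below 8 g/dL during the 21-day DLT period, discontinuation follows Section 5.1.7.2.* Leave 5.1.3.3 and 5.1.7.2 unchanged, and keep the other anemia guidance in 6.5.4.4.

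A cross-reference is better than changing the joining word in the bullet. The bullet covers any Hgb below 8 g/dL, whereas 5.1.7.2 concerns Grade 3 drug reactions and has a separate rule for Grade 4. A reworded bullet would keep that mismatch in scope.

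The cost is one sentence, with no change to the DLT definition and no added subjects, visits or tests. The edit does not settle the retreatment question, which needs its own clarification.

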6.5.4.5 Rash with Hyperkeratosis/Keratoacanthoma/Squamous Cell Carcinoma of the Skin

Monitoring will include skin assessments as defined in the Schedules of Assessments (Table 1 and Table 2), with biopsy of suspicious lesions. Management should be discussed with the Medical Monitor on a case-by-case basis. Dermatological consults should be requested as needed. Hyperkeratotic rash/keratoacanthoma/squamous cell carcinoma will be considered as AESI requiring expedited reporting from the Investigator to the Sponsor.

6.5.4.6 Alterations in Wound Healing or Tissue Damage Repair

Management should be discussed with the Medical Monitor on a case-by-case basis. Dermatological consults should be requested as needed.

CONFIDENTIAL INFORMATION

6.5.4.7 Dose Interruptions for Adverse Events No Related to Study Drug

In the case of Grade 3 and Grade 4 AEs that are not considered to be related to the study drug, the study treatment may be interrupted based on the Investigator assessment. The subject will be medically treated for the event.

If the AE reduces to a lower tolerable grade, the study treatment may be resumed in the subsequent cycle. If the AE remains the same in spite of medical treatment until the next treatment (second cycle after the AE occurred), the event should be discussed with the Medical Monitor to consider either a possible extension of the dose interruption for up to 1 additional cycle or a permanent withdrawal from the study treatment.

If upon resuming study treatment, the subject experiences the same AE again, this should be discussed again with the medical monitor to assess permanent withdrawal from the study treatment.

Grade 3 and 4 laboratory abnormalities that do not have clinical significance do not require dose interruption.

6.6 Packaging and Labeling of the Investigational Medicinal Product

[figure not shown]
MSB0011359C freeze-dried formulation is presented at a concentration of 45 mg/vial in USP / Ph Eur type I glass vial closed with a rubber stopper and sealed with an aluminum crimping cap. MSB0011359C liquid formulation is presented at a 10 mg/mL concentration in a USP / Ph Eur type I 50R vial closed with a rubber stopper and sealed with an aluminum crimp seal closure. The stopper is made of elastomer complying with USP and Ph Eur. Vials are filled with 61.2 mL of drug product solution in order to allow an extractable volume of 60 mL.

Packaging and labeling will be in accordance with applicable local regulatory requirements and applicable Good Manufacturing Practice guidelines. MSB0011359C will be packed in boxes containing a suitable number of vials. The information on the medication will be in accordance with approved submission documents.

MSB0011359C will be shipped in transport cool containers (2°C to 8°C) that are monitored with temperature control devices.

Packaging and labeling will be in accordance with applicable local regulatory requirements and applicable GMP Guidelines.

6.7 Preparation, Handling and Storage

Detailed information on infusion bags and medical devices to be used for the preparation of the dilutions and subsequent administration will be provided in the manual of preparation.

MSB0011359C must not be used for any purpose other than the trial. The administration of IMPs to subjects who have not been enrolled into the trial is not covered by the trial insurance.

The contents of the MSB0011359C vials are sterile and non-pyrogenic, and do not contain bacteriostatic preservatives. Any spills that occur should be cleaned up using the facility's standard cleanup procedures for biologic products.

Any unused portion of the solution should be discarded in biohazard waste disposal with final disposal by accepted local and national standards of incineration.

